2.2.2 Dosing Rationale

The optimal dose and dosing regimen for dMAb AZD5396 (mAb AZD2130 encoded via DNA plasmid) and dMAb AZD8076 (mAb AZD2196 encoded via DNA plasmid) are as yet uncharacterized. In addition to safety, this study will assess 4 different doses to evaluate the pharmacokinetic profile of mAb AZD5396 and mAb AZD8076 expression following administration of dMAb AZD5396 and dMAb AZD8076. Preclinical studies of dMAb AZD5396 and dMAb AZD8076 in rhesus macaques assessed a 2 mg dose and demonstrated clinically detectable levels of mAb AZD5396 and mAb AZD8076 in the circulation for up to 49 days following the last dose of AZD5396 and AZD8076.

The dose was selected to deliver the maximum amount of plasmid DNA within the volume and concentration limitations of the final product and available animal data. Five doses will be tested, ranging from 0.25 to 4 mg, in 8 cohorts.

Electroporation using the CELLECTRA™ 2000 device with side port needle will follow seconds after injection of the dose.

2.2.3 **Rationale for Electroporation**

Several groups are developing methods to improve the expression of DNA-based therapeutic proteins and vaccines, using genetic optimization (including use of highly concentrated DNA formulations, multiple RNA optimizations, and addition of improved leader sequences) and alternative cellular delivery (i.e. EP)¹². Electroporation is a physical process that exposes the target tissue to a brief electric field pulse that induces temporary and reversible pores in the cell membrane to enhance the cellular uptake of large molecules such as DNA. By temporarily increasing the permeability of cell membranes, EP has been shown to be an efficient way to introduce DNA into cells^{13,14} and to increase the expression level of antigens encoded by DNA¹⁵. This technology has been used for more than three decades by molecular biologists for in vitro cell transfection and is now being employed by Inovio in the clinic for delivery of plasmid DNA vaccines and immunotherapies.

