4 STUDY PLAN

4.1 Study Design

This will be a Phase 1, open label, single center, dose escalation study to evaluate the safety, tolerability, and pharmacokinetic profile of mAb AZD5396 and mAb AZD8076 following delivery of optimized dMAb AZD5396 and dMAb AZD8076 with different doses of Hylenex® Recombinant, administered by intramuscular injection (IM) followed immediately by electroporation (EP) using the CELLECTRA™ 2000 with side port needle device, in a five-dose (8 cohort) regimen in healthy adults.

Up to 50 healthy volunteers 18 to 60 years of age will be enrolled in this study and evaluated across eight cohorts (n=3 to 6 per cohorts A1, A2, B, C, and D; n=5 per cohorts E, F, and G). Participants will be administered dMAb AZD5396 and dMAb AZD8076 at a five-dose level of each plasmid:

- 0.5 mg single-dose (cohort A1),
- 1 mg single-dose (cohort A2),
- 1 mg two-dose (cohorts B and F),
- 2 mg two-dose (cohort C),
- 0.25 mg two-dose (cohort D),
- 4 mg two-dose (cohort E), and
- 2 mg four-dose (cohort G).

Participants will receive two injections (one per dMAb) into the arm (deltoid)/leg (quadriceps) region at Day 0 alone (groups A1 and A2) or on day 0 and 3 (groups B-F) or on days 0, 3, 28, 31 (cohort G). Injections may be given in different arms or in an arm (deltoid) and a leg (quadriceps). If preferred or needed both doses can be done in the deltoid region or the lateral quadriceps, although the injections should be in different areas separated by at least 2 cm. The Day 3 injections may repeat an area already used on Day 0 as long as separated by at least 2 cm. The Day 31 injections may repeat an area already used on Day 28 as long as separated by at least 2 cm. The Day 28 injections may repeat an area already used on Day 0 or Day 3 injections with no separation required given the time span between injections.

This study will adhere to a dose escalation scheme as described in [Figure 2](#).

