D	dMAb AZD5396 and dMAb AZD8076	Day 0, 3	6 (3+3)	2x (0.25 mg dMAb AZD5396) + 2x (0.25 mg dMAb AZD8076)	34U	0.25 mL	OpBlock 0078	0.5 mg dMAb AZD5396 + 0.5 mg dMAb AZD8076
E	dMAb AZD5396 and dMAb AZD8076	Day 0, 3	5	2x (2 mg dMAb AZD5396) + 2x (2 mg dMAb AZD8076)	75U (0.5 mL)	0.70 mL	OpBlock 0078	4 mg dMAb AZD5396 + 4 mg dMAb AZD8076
F	dMAb AZD5396 and dMAb AZD8076	Day 0, 3	5	2x (0.5 mg dMAb AZD5396) + 2x (0.5 mg dMAb AZD8076)	75U (0.5 mL)	0.55 mL	OpBlock 0070	1 mg dMAb AZD5396 + 1 mg dMAb AZD8076
G	dMAb AZD5396 and dMAb AZD8076	Day 0, 3, 28, 31	5	4x (0.5 mg dMAb AZD5396) + 4x (0.5 mg dMAb AZD8076)	75U (0.5 mL)	0.55 mL	OpBlock 0078	2 mg dMAb AZD5396 + 2 mg dMAb AZD8076
	TOTAL		44-50^d					

^a All subjects will receive the study product by IM route of administration. All doses of optimized dMAb AZD5396 and dMAb AZD8076 will be prepared with Hylenex® less than 4 hours before dosing of subjects. Doses of Hylenex will vary depending on the cohort to allow for a different volume per injection

^b Use of CELLECTRA™ 2000 with Side Port needle, OpBlock 0078 and 5P-IM Side Port Array or Profusion Therapeutic Infusion needle (G47574) for Cohorts A-E & G.

^c Use of CELLECTRA™ 2000 with Side Port needle, OpBlock 0070 and 5P-IM Side Port Array for Cohort F.

^d Note that the n is defined as evaluable participants. Due to partial doses or early dropouts, we may dose up to 50 participants total to reach enough evaluable participants in each cohort. See Protocol section [8.2](#) which describes replacing participants.

The decision to open new cohorts in the clinical trial is justified by several key factors. Firstly, ensuring safety is of utmost importance in any clinical trial. By introducing additional cohorts, we will gather more data on the safety profile of the investigational product.

Secondly, evaluating the levels of expression of dMAbs is crucial for assessing the efficacy of this approach. The expression levels directly impact the therapeutic potency and effectiveness *in vivo*. By expanding the cohorts, we will gather a larger sample size and thereby obtain more reliable data on the expression levels of dMAbs in different individuals. This broader understanding of expression levels will aid in determining optimal dosages and predicting the treatment's potential success.

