4.2 Dose Escalation Scheme

The study will apply a single ascending dose (SAD) modified 3+3 design. This study will adhere to a dose escalation scheme as described in [Figure 2](#). Participants will be enrolled sequentially beginning with Cohort A1. The first participant in cohort A1 will be dosed on Day 0 following confirmation of eligibility criteria. If no stopping event (DLT) is observed (see [Section 10.10](#)) after 14 days of the initial dose, the remaining two participants in that cohort will be dosed. If there are 0 DLT events after 14 days of the initial dosing of the third subject, enrollment will be completed, and then cohort A2 will open. Same process will be followed for cohorts B and C. Because cohorts D, F, & G are a similar or lower dose and the safety profile would have been already established in previous cohorts, the 14-day waiting periods will not apply to Cohorts D, F, or G. Even though the levels of expression observed in cohorts

A-D are way below the levels seen when the monoclonal antibodies are given as protein, Cohort E will receive a higher dose which will require a 14 day waiting period after the dosing of the first participant at this level. Every participant in Cohort E following the 14 day waiting period will be dosed 3 days apart as in other cohorts.

If one dose limiting toxicity (DLT) is observed in the first three participants enrolled in any cohort, an ad hoc DSMB will review the event and make a decision if the study should continue. If the DSMB agrees that the study should continue, the remaining participants will be enrolled in the cohort and dosed but the next cohort will not open until the 28-day period of safety is completed. However, if any additional DLT occurs (i.e., >1 DLT in 6 total participants in a given cohort), then that dose will be deemed not tolerated.

Figure 2. Dose Escalation Scheme

Doses of Investigational product will be administered intramuscularly in ~0.5 mL/dose volume in cohorts A1, B, F, & G; ~1 mL/dose volume in cohorts A2 & C; ~0.25 mL/dose volume in cohort D; and ~2 mL/dose volume in cohort E, followed immediately by EP with the CELLECTRA™ 2000 with Side Port needle device. It is recommended that the investigational product be administered such that the injection is delivered slowly using the side port needle in muscle. The side port needle should be fully

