6.1.4 Handling, Preparation and Dispensing of dMAb AZD5396 and dMAb AZD8076

Investigational product is to be prepared by site staff who are trained and knowledgeable in mixing and dispensing investigational agents. For details, please review the Pharmacy Manual. Documentation of certification will be kept with the pharmacy documents. Study drug should be prepared in a BioSafety level 2 cabinet. Personnel will utilize proper aseptic technique per institutional guidelines.

It is the responsibility of the Investigator to ensure that dMAb AZD5396 and dMAb AZD8076 and CELLECTRA™ are only dispensed and administered to study participants. Authorized personnel at the official study site must be the only ones to dispense the product according to local regulations.

dMAb AZD5396 (pGX93321 and pGX93311) and dMAb AZD8076 (pGX93322 and pGX93315) drug products are formulated in a saline sodium citrate (SSC) buffer to a concentration of 10 mg/mL plasmid in 150 mM sodium chloride and 15 mM sodium citrate, which is supplied in 2 R glass vials and stored refrigerated at 5°C. Hylenex® Recombinant (human hyaluronidase injection) will be used for dose preparation at the clinical site. Hylenex® is approved in the US for intramuscular use to increase the dispersion and absorption of other injected drugs. In this Phase 1 clinical study, a 0.5 to 2 mg dose of dMAb AZD5396 and dMAb AZD8076 will be administered intramuscularly.

Dose preparation of each investigational product will occur within 4 hours prior to administration. For details about the preparation of the dose, consult the most current version of the Pharmacy Manual.

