11.3 Description of Statistical Methods

11.3.1 Safety Analyses Adverse Events

All solicited and unsolicited AEs/SAEs will be summarized by frequency per cohort and for all cohorts combined. These frequencies will be presented separately by dose and overall, by system organ class and by preferred term, the number and percentage of participants affected. Percentages, along with associated exact 90% Clopper-Pearson confidence intervals, will be based on the number of participants who are members of the safety analysis. Additional frequencies will be presented with respect to maximum severity and to strongest relationship to Investigational product administration. Multiple occurrences of the same AE will be counted only once following a worst-case approach with respect to severity and relationship to Investigational product. All SAEs and administration site events will also be summarized as above.

The main summary of safety data (treatment emergent) will be based on events occurring within 48 weeks of administration of at least one of the investigational products (as specified in Section 10.12). Safety data will also be summarized based on events occurring any time after administration of Investigational product on Day 0 to week 72.

Laboratory Data and Vital Signs

Continuous response variables per time point and changes from baseline will be summarized with descriptive statistics: mean standard deviation, minimum, median, and maximum values by time point and cohort. Categorical response variables will be summarized per time point and cohort with frequencies and percentages.

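### Cohort E's injection volume is 0.70 mL in Table 2 but about 2 mL in Section 4.2; as a minor related point, the dose labels mix two scales

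*Protocol*

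**What the plan says.** **Volume.** The cohort E row of Table 2 (Section 4.1) lists "2x (2 mg dMAb AZD5396) + 2x (2 mg dMAb AZD8076"), 75 U of Hylenex in 0.5 mL per injection, and a final volume of 0.70 mL per injection. Section 4.2 lists volumes again, cohort by cohort: "0.5 mL/dose volume in cohorts A1, B, F, & G; ~1 mL/dose volume in cohorts A2 & C", then "0.25 mL/dose volume in cohort D; and ~2 mL/dose volume in cohort E".

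**Dose.** The list in Section 4.1 describes cohort D as "0.25 mg two-dose (cohort D"), while Table 2 gives that cohort "2x (0.25 mg dMAb AZD5396) + 2x (0.25 mg dMAb AZD8076"), a total of 0.5 mg of each product. Section 2.2.2 first says that four doses will be assessed and then "Five doses will be tested, ranging from 0.25 to 4 mg, in 8 cohorts". Section 6.1.4 says that "a 0.5 to 2 mg dose of dMAb AZD5396 and dMAb AZD8076 will be administered intramuscularly". In the analysis sections, Section 11.2 assigns safety-set participants by dose level and cohort. Section 11.3.1 summarises adverse events per cohort and adds "These frequencies will be presented separately by dose and overall", without naming a dose scale.

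**The concern.** Both volume statements are current text, and they describe the same cohort. Cohort E receives the largest amount of plasmid, and it is the one later cohort for which the protocol keeps a 14-day wait after the first participant. If the milligram amount is held at Table 2's 2 mg, the two volumes imply plasmid concentrations of 2.86 and 1.0 mg/mL. The protocol should not leave that open for the cohort meant to show what a higher dose does to safety and expression.

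The dose wording matters less. Sections 11.2 and 11.3.1 use dose as a grouping, and the protocol describes dose on two scales without saying so. The number of levels and the cohorts pooled in each therefore depend on which section is followed.

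**Working it through.** **1. Reproduce Table 2's volumes.** Inputs: drug product at 10 mg/mL (Section 6.1.2); Hylenex at 75 U in 0.5 mL, so 150 U/mL (Table 2, cohorts E to G). For cohorts A1 to D, Table 2 gives Hylenex in units only, so the 150 U/mL strength is assumed to apply there too.

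Volume per injection = mg / 10 + Hylenex units / 150.

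| Cohort | Calculation (mL) | Result | Table 2 | Section 4.2 | 4.2 / Table 2 |
|---|---|---|---|---|---|
| A1 | 0.05 + 68/150 | 0.503 | 0.5 | ~0.5 | 1.00 |
| A2 | 0.10 + 135/150 | 1.000 | 1 | ~1 | 1.00 |
| B | 0.05 + 66.5/150 | 0.493 | 0.5 | ~0.5 | 1.00 |
| C | 0.10 + 135/150 | 1.000 | 1 | ~1 | 1.00 |
| D | 0.025 + 34/150 | 0.252 | 0.25 | ~0.25 | 1.00 |
| E | 0.20 + 75/150 | 0.700 | 0.70 | ~2 | 2.86 |
| F | 0.05 + 75/150 | 0.550 | 0.55 | ~0.5 | 0.91 |
| G | 0.05 + 75/150 | 0.550 | 0.55 | ~0.5 | 0.91 |

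All eight Table 2 volumes are reproduced after rounding. The volume in Section 4.2 is the per-injection volume, exact or rounded, for every cohort except E.

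**2. Try other readings of cohort E.**
- One injection: 0.70 mL.
- Both injections on one day: 2 x 0.70 = 1.4 mL.
- Both injections of one product over the regimen: 2 x 0.70 = 1.4 mL.
- All four injections: 4 x 0.70 = 2.8 mL.

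None is about 2 mL.

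**3. Dose scale.** Total = mg per injection of each product x number of dosing days.

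| Cohort | Per injection (mg) | Days | Total (mg) | Section 4.1 label (mg) |
|---|---|---|---|---|
| A1 | 0.5 | 1 | 0.5 | 0.5 |
| A2 | 1 | 1 | 1 | 1 |
| B | 0.5 | 2 | 1 | 1 |
| C | 1 | 2 | 2 | 2 |
| D | 0.25 | 2 | 0.5 | **0.25** |
| E | 2 | 2 | 4 | 4 |
| F | 0.5 | 2 | 1 | 1 |
| G | 0.5 | 4 | 2 | 2 |

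- Distinct totals: 0.5, 1, 2, 4 mg (four levels).
- Distinct per-injection amounts: 0.25, 0.5, 1, 2 mg (four levels).
- Distinct labels: 0.25, 0.5, 1, 2, 4 mg (five levels, only because D's label is on the other scale).
- The 0.5 to 2 mg range in Section 6.1.4 fits neither scale: it leaves out D per injection (0.25 mg) and E in total (4 mg).

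**4. Effect on a table by dose,** using the n in Table 2's rows:
- By total: A1 and D (3 + 6 = 9); A2, B and F (3 + 6 + 5 = 14); C and G (6 + 5 = 11); E (5).
- By injection: D (6); A1, B, F and G (3 + 6 + 5 + 5 = 19); A2 and C (3 + 6 = 9); E (5).
- By Section 4.1 label: as by total, but with D (6) and A1 (3) separate.

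**The case against.** The strongest reply is that Table 2 already settles most of this. It gives milligrams per injection, Hylenex, volume and total milligrams for every cohort, and its amounts are consistent. Cohort E's dose of 2 x 2 mg, 4 mg in total, is the same in Table 2 and the Section 4.1 list. Preparation is referred to the Pharmacy Manual, which is not at hand and may state one volume clearly. The scale for a descriptive table can be left to the statistical analysis plan. All of this stands and limits the point, but a protocol with two volumes for one injection still needs correcting.

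A reader might infer more than the documents support:

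- *That cohort E's dose is undefined, or that its Hylenex amount is in conflict.* Only the volume is. Section 4.2 states no Hylenex amount, so the 75 U is uncontradicted. Table 2 puts cohorts A1 to D at about 1 mg/mL, and 2 mg at that ratio would fill 2 mL. With 0.2 mL of plasmid this would need 1.8 mL of Hylenex, or 270 U at 150 U/mL. That is a possible origin of the figure, but the protocol does not say so.
- *That participants could receive about 2 mL, or that dosing of cohort E is under way and needs a condition placed on it.* The document shows neither.
- *That a primary analysis is undefined.* The primary safety objective is stated per study group, the by-dose split is not called primary, and PK detection is summarised within cohort. By dose might even mean by dosing occasion.
- *That cohort D standing alone below A1 shows harm from mixed labels.* It also stands alone on a consistent per-injection scale. Nothing says that the Section 4.1 labels will define the strata.

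**Conclusion.** The volume contradiction holds and should be corrected: 0.70 mL against about 2 mL per injection for the highest-dose cohort, a 2.9-fold difference that rounding, units or counting several injections together does not explain. The cohort E arithmetic rests only on figures in the protocol. The assumed 150 U/mL for cohorts A1 to D matters only to the reproduction of their rows. That 0.70 mL follows from Table 2's components shows that Table 2 is self-consistent; it does not decide which volume the sponsor intends.

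The dose-scale inconsistency is real but minor. One label is on a different scale from those of the other multi-dose cohorts, and the statements of four doses, five doses from 0.25 to 4 mg, and 0.5 to 2 mg cannot all hold on one scale. The statistical analysis plan could name the scale for a by-dose table, but it would not correct those protocol statements. Cohort E's milligram dose and the per-cohort safety summaries are unaffected.

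**What to change.** - Reconcile Section 4.2 and Table 2 on cohort E's volume, and check both against the Pharmacy Manual. The choice of value is the sponsor's.
- In the same amendment, name one dose scale (per injection or total) and bring the Section 4.1 list, both counts in Section 2.2.2 and the range in Section 6.1.4 into line with it. Table 2 already shows both quantities and can serve as the reference.
- Use the named scale wherever Sections 11.2 and 11.3.1 group by dose, or say there that the statistical analysis plan will define it.

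The cost is wording in the protocol and, if it differs, in the Pharmacy Manual. Reconciling the text does not alter the sample size, the visit schedule or the per-cohort analyses.

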5 STUDY POPULATION

5.1 Inclusion Criteria

1. Age 18-60 years.
2. Able to provide consent to participate and having signed an Informed Consent Form (ICF).
3. Able and willing to comply with all study procedures.
4. Body mass index (BMI) between 20 and 31, inclusive.
5. Screening laboratory must be within normal limits or have only Grade 0-1 findings.
6. Normal screening ECG or screening ECG with no clinically-significant findings.
7. Women of child-bearing potential agree to one of the following:
 - a. use medically effective contraception (oral contraception, barrier methods, spermicide, etc.)
 - b. have a partner who is sterile from enrollment to 6 months following the last injection
 - c. have a partner who is medically unable to induce pregnancy

Abstinence is acceptable per Investigator discretion and as long as it is documented that the subject will use medically effective contraception when engaging in sexual activities and notifies the study team.

8. Sexually active men who are considered sexually fertile must agree to one of the following:
 - a. use a barrier method of contraception during the study and continue its use for at least 6 months following the last injection
 - b. have a partner who is permanently sterile or is medically unable to become pregnant
9. No history of clinically significant immunosuppressive or autoimmune disease. Individuals with HIV infection who have been virologically suppressed for more than 1 year and with current CD4 cell count entry greater than 500 cells/ μ l will be allowed into the study.

5.2 Exclusion Criteria

1. Administration of an investigational compound either currently or within 6 months of first dose.
2. Administration of any vaccine within 4 weeks of first dose.
3. Administration of a SARS-CoV-2 vaccine in the last 14 days or plans to have any standard of care vaccines within 14 days from the last administration of study products.
4. Positive SARS-CoV-2 infection at screening visit.
5. Administration of any monoclonal or polyclonal antibody product within 4 weeks of the first dose.

6. Administration of any blood product within 3 months of first dose.
7. Co-morbid conditions including poorly-controlled diabetes (HbA1C > 7), poorly-controlled hypertension (BP > 140/95 repeatedly), asthma, and any cardiovascular disease.
8. Pregnancy or breast feeding or plans to become pregnant during the course of the study.
9. Positive serologic test for hepatitis B surface antigen (HBsAg); or any potentially communicable infectious disease as determined by the Principal Investigator or Medical Director.
10. Positive serologic test for hepatitis C (exception: successful treatment with confirmation of sustained virologic response);
11. Baseline evidence of kidney disease as measured by creatinine greater than 1.5 mg/dL (CKD Stage II or greater);
12. Baseline screening lab with Grade 2 or higher abnormality, except for Grade 2 creatinine.
13. Chronic liver disease or cirrhosis.
14. Immunosuppressive illness including hematologic malignancy, history of solid organ or bone marrow transplantation.
15. Current or anticipated concomitant immunosuppressive therapy (inhaled, topical skin and/or eye drop-containing corticosteroids, low-dose methotrexate, or prednisone at a dose less than 10 mg/day or steroid dose-equivalent are not exclusionary).
16. Current or anticipated treatment with TNF- α inhibitors such as infliximab, adalimumab, etanercept.
17. Prior major surgery or any radiation therapy within 6 months of first dose.
18. Any pre-excitation syndromes, e.g., Wolff-Parkinson-White syndrome.
19. Presence of a cardiac pacemaker or automatic implantable cardioverter defibrillator (AICD)
20. Fewer than two acceptable sites available for IM injection and EP considering the deltoid and anterolateral quadriceps muscles. The following are unacceptable sites:
 - a. Tattoos, keloids or hypertrophic scars located within 2 cm of intended administration site.
 - b. Implantable-Cardioverter-defibrillator (ICD) or pacemaker (to prevent a life-threatening arrhythmia) that is located ipsilateral to the deltoid injection site (unless deemed acceptable by a cardiologist).
 - c. Any metal implants or implantable medical device within the electroporation site.
21. Prisoner or participants who are compulsorily detained (involuntary incarceration) for treatment of either a physical or psychiatric illness.
22. Active drug or alcohol use or dependence that, in the opinion of the investigator, would interfere with adherence to study requirements or assessment of immunologic endpoints.
23. Not willing to allow storage and future use of samples for SARS-CoV-2 virus related research.
24. Any illness or condition that in the opinion of the investigator may affect the safety of the participant or the evaluation of any study endpoint.
25. Participants with known bleeding diatheses or that are using blood thinners for 30 days before study enrollment including warfarin, heparin, Clopidogrel, Apixaban (Eliquis), Dabigatran

(Pradaxa), Edoxaban (Savaysa), Rivaroxaban (Xarelto). The use of low dose aspirin (81 mg daily) is acceptable.

26. Participants with concomitant intramuscular medications.

